**Table 2-2 Liver-related events**

Parameter	Criterion
ALT	>3xULN; >5xULN; >8xULN;>10xULN
AST	>3xULN; >5xULN; >8xULN >10xULN;
ALT or AST	>3xULN; >5xULN; >8xULN >10xULN;
ALT or AST and TBL	ALT or AST > 3 × ULN and TBL > 2 x ULN ALT or AST > 5 × ULN and TBL > 2 x ULN ALT or AST > 10 × ULN and TBL > 2 x ULN
TBL	>1.5xULN, >2xULN
ALP	>2xULN, >3xULN
ALP & TBL	ALP >3xULN & TBL >2xULN
(ALT or AST) & TBL & ALP	ALT or AST >3xULN & TBL >2xULN & ALP <2xULN ( Hy's Law )

To support the primary endpoint, the number and percentage of patients with at least 2 CTCAE grades increase from baseline in ALT or AST at any time during the study will be provided by cohort and treatment. This safety endpoint will be analyzed using the method specified in [Section 2.5.2](#).

Peak ALT/AST and peak TBL will be plotted using eDISH (evaluation of Drug Induced Serious Hepatotoxicity) method and Modified eDISH (mDISH) method, see Lin, *et. al.* (2012).

If required for SRC, maximum increases in ALT or AST during the first 2 weeks (Day 1 to Day 15) will be categorized based on the Protocol Table 3-1 as follows:

- 2:  $\geq 2$  CTCAE grades increase from baseline in either ALT or AST
- 1: 1 CTCAE grades increase from baseline if baseline value is normal or  $\geq 2$  times baseline value if baseline value is above normal in either ALT or AST
- 0: otherwise.

Listing of patients with the following renal related laboratories will be provided:

- Serum creatinine increase 25 – 49% compared to baseline
- Serum creatinine increase  $\geq 50\%$  compared to baseline
- New dipstick proteinuria  $\geq 1+$
- New dipstick hematuria  $\geq 1+$
- New dipstick glycosuria  $\geq 1+$

For urinalysis, frequency tables will be presented. Number and percent of patients in each category will be presented for each visit.

Urine pregnancy data will be summarized by visit.

Laboratory measurements, which are recorded as below the assay detection limits, will be imputed as half of the detection limit; and that above the detection limit will be imputed as detection limit, for the summary statistics.

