3.1 Study design

This will be a multicenter, open label, randomized, dose escalation study to evaluate the hepatic safety and tolerability of KAE609 in adult patients (≥ 18 years and ≥ 45 kg bodyweight) with uncomplicated malaria caused by *P. falciparum*.

Starting dose of KAE609 will be a single dose of 10 mg and following acceptable safety results in the 10 mg treatment arm, the dose of KAE609 will be increased stepwise up to a single dose of 225 mg and multiple doses of 50 mg (QD x3 days) according to schedule below (Figure 3-1).

Based on the safety pattern observed in previous studies with KAE609, LFT parameters, if they rise, are expected to peak within 14 days of treatment. Hence, the decision to escalate to next cohort with higher doses will be based on the criteria as specified in the table below (Table 3-1):

Table 3-1 Decision criteria for dose escalation based on LFT results with KAE609

LFT parameter	Baseline	Maximum post baseline value	Decision to escalate to next cohort
ALT/AST	Within ULN	< 2 times ULN (from Day 1 to Day 15)	Escalate to next cohort after notification to safety review committee, after all the patients in the cohort have been followed for at least 14 days post treatment (study Day 15).
	> 1 to ≤ 1.5 ULN	< 2 times baseline (from Day 1 to Day 15)	
ALT/AST	Within ULN	≥ 2 to < 3 times ULN (from Day 1 to Day 15)	Escalate to next cohort based on review of liver safety (and any other relevant data) by safety review committee, after all the patients in the cohort have been followed for at least 28 days post treatment (Study Day 29)
	> 1 to ≤ 1.5 ULN	≥ 2 to < 3 times baseline (from Day 1 to Day 15)	
ALT/AST	Any baseline value	≥ 2 Grade (CTCAE grades) increase from baseline (at any time point during the study) in: 
 - 2 patients in a 10 patient cohort (Cohorts 1 and 2) or - 3 patients in a 20 patient cohort (Cohorts 3, 4, 5 and 6) 	Suspend recruitment and initiate review of liver safety (and any other relevant data) by safety review committee. Any further progression of the study is based on the decision by the safety review committee.

[figure not shown]
In consultation with the safety review committee, Novartis can suspend recruitment and trigger safety review any time based on safety signals including any potential Hy's law case.

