9.5.2.2 Laboratory evaluations

Summary of laboratory evaluations will be presented with respect to three groups of laboratory tests (hematology, blood chemistry, and urinalysis).

Descriptive summary statistics (mean, median, standard deviation, minimum and maximum) for the baseline, each study visit, and change from baseline to each study visit will be presented. These descriptive summaries will be presented by laboratory test group.

In addition, shift tables will be provided in order to compare a patient's baseline laboratory evaluation relative to each study visit and at the maximum value. For the shift tables, the normal laboratory values will be used to evaluate whether a particular laboratory test value is normal, low, or high for each visit value relative to whether or not the baseline value is normal, low, or high. For liver enzymes (ALT, AST, etc.), the shift table of CTCAE grades relative baseline and number and percent of patients with $\geq 2 \times$ ULN (if baseline is normal) or $2 \times$ baseline (if baseline is $>$ ULN) will be provided. These summaries will be presented by laboratory test group.

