**Table 2-6 Specification of data outputs for SRM data review**

Output	Analysis set	Periodic safety review
Baseline		
Demographic characteristics	FAS	Yes
Background disease characteristics	FAS	Yes
Safety		
Concomitant medications/significant non-drug therapies	Safety	Yes
Relevant medical history/current medical condition	Safety	
All adverse events and Serious adverse events	Safety	Yes
Newly occurring liver enzyme abnormalities (categorical analysis)	Safety	Yes
Clinical chemistry shift table based on CTC grade	Safety	Yes
ALT & AST meeting specified criteria during first 2 weeks	Safety	Yes
eDISH and mDISH plots	Safety	Yes

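### For a normal baseline, the SAP's committee category 1 for ALT/AST uses a one-grade CTCAE rise where Protocol Table 3-1 uses 2 × ULN, and the protocol's count at 2 × ULN is dropped without being declared

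*SAP*

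**What the plan says.** **Protocol Table 3-1** (section 3.1, repeated as SAP Table 1-1) sets the escalation route.

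- Row 1, normal baseline: "< 2 times ULN (from Day 1 to Day 15". The next cohort opens after the committee is notified, once all patients have reached Day 15.
- Row 2, normal baseline: "≥ 2 to < 3 times ULN (from Day 1 to Day 15". Escalation waits for committee review, after all patients have reached Day 29. For a baseline above 1 and up to 1.5 × ULN, the row 2 limit is "≥ 2 to < 3 times baseline (from Day 1 to Day 15".
- Row 3: a rise of two or more CTCAE grades "at any time point during the study", in 2 patients (10-patient cohorts) or 3 patients (20-patient cohorts). Recruitment is suspended for review.

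**SAP 2.8.2**, in the text after Table 2-2, says that if the committee needs it, "maximum increases in ALT or AST during the first 2 weeks (Day 1 to Day 15) will be categorized" on the basis of Protocol Table 3-1. Category 2 is a rise of two or more grades. Category 1 is "1 CTCAE grades increase from baseline if baseline value is normal", or at least 2 × baseline if the baseline is above normal. Category 0 is everything else.

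**SAP Table 2-6** lists "ALT & AST meeting specified criteria during first 2 weeks" as a periodic-review output, without restating the criteria.

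**Protocol 9.5.2.2** provides, for liver enzymes, "the shift table of CTCAE grades relative baseline and number and percent of patients with" a value of at least 2 × ULN (normal baseline) or 2 × baseline (baseline above ULN). SAP 2.8.2 keeps the shift table. In SAP Table 2-2 the lowest ALT/AST limit is above 3 × ULN; the 2 × ULN entries there concern bilirubin and ALP.

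**SAP section 4**, on changes to protocol-specified analyses, reads NA.

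**The concern.** The SAP names Table 3-1 as its source but changes the limit in the limb that covers every patient with a normal baseline. A CTCAE grade and a multiple of ULN are different scales. They agree here only if grade 1 starts exactly where row 2 starts. If it starts lower, one category holds two groups that the protocol sends down different routes, and the 2 × ULN limit cannot be read from the display.

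The protocol's own count at 2 × ULN would fill that gap, but it is absent from the SAP and its removal is not recorded. Hepatic safety is the primary objective, so an undeclared loss of a planned liver summary matters for the final report as well as for interim review.

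**Working it through.** **1. The plan's own figure.** Protocol 9.8.1 and SAP 3.1 give operating characteristics for the two-grade rule. With P(X ≥ r) = 1 − Σ C(n,k) p^k (1−p)^(n−k), summed over k < r:

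- n = 10, r = 2: 0.851 at p = 30% and 0.0345 at p = 3%.
- n = 20, r = 3: 0.965 at p = 30% and 0.0210 at p = 3%.

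These reproduce the stated values (above 80%, above 90%, below 5%). They concern row 3 only, and the point here does not depend on them.

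**2. Assumption.** SAP 5.4 grades by CTCAE version 4.0, but neither document prints the limits. I assume grade 1 runs from above ULN to 3 × ULN, grade 2 to 5 × ULN and grade 3 to 20 × ULN. The start of grade 1 is then varied from 1.0 to 2.0 × ULN.

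**3. Normal baseline, grade 1 starting at 1.0 × ULN.**

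| Day 1–15 peak (× ULN) | Protocol Table 3-1 | SAP category |
|---|---|---|
| 0.9 | row 1 | 0 |
| 1.05, 1.2, 1.5, 1.9, 1.99 | row 1 | 1 |
| 2.0, 2.5, 2.9 | row 2 | 1 |
| 3.1 and above | two-grade rise (row 3 criterion) | 2 |

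Category 1 merges part of row 1 with all of row 2. No row 2 value falls in category 0.

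**4. Varying the start of grade 1.**

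| Assumed start (× ULN) | Row 1 peaks placed in category 1 | Row 2 peaks placed in category 0 |
|---|---|---|
| 1.0 | above 1.0 to below 2.0 | none |
| 1.25 | above 1.25 to below 2.0 | none |
| 1.5 | above 1.5 to below 2.0 | none |
| 2.0 | none | only the boundary value 2.0 itself |

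Within this range, the two rules agree only when grade 1 starts at 2 × ULN.

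**5. Baseline above normal.** At baselines of 1.2 and 1.5 × ULN, row 1 matched category 0 and row 2 matched category 1 at every value tested. The SAP limb has no upper limit. A peak of 4.0 × ULN from 1.2 × ULN (ratio 4.0/1.2 = 3.33, one grade) is therefore category 1, although it fits no row of Table 3-1.

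**6. How often over-flagging could show.** Assume that a share q of KAE609 patients has a normal baseline and peaks between 1 and 2 × ULN, that nobody goes higher, and that grade 1 starts at 1.0 × ULN. The cohort then belongs in row 1. The chance of at least one category 1 patient is 1 − (1 − q)^n.

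| KAE609 patients | q = 5% | q = 20% |
|---|---|---|
| 10 | 40% | 89% |
| 20 | 64% | 99% |
| 40 (two arms of 20) | 87% | above 99% |

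The values of q are illustrative; the documents give none.

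**7. The omitted count.** This needs no grade limits. Protocol 9.5.2.2 names the count in addition to the shift table. The SAP has the shift table, no ALT/AST limit below 3 × ULN in Table 2-2, and NA in section 4.

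**The case against.** The strongest reply is that the 0/1/2 display is a minor tool. It applies only if the committee requires it. SAP 2.15 has the decision-makers work from data management's review reports, with laboratory data monitored continuously. SAP Table 1-1 repeats the Table 3-1 limits in full, and the criteria mentioned in Table 2-6 may mean that table. The committee charter and output shells, which could settle this, are not among the documents. Under the assumed limits the error is also cautious: it prompts extra review and hides no row 2 patient.

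Most of this stands, and it rules out three stronger readings that a reader might infer.

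- *The committee would decide escalation from this table alone.* The documents do not say so; the review reports and Table 1-1 are also available.
- *Rises on Days 16–29 are missed.* They are not. SAP 2.8.2 also requires the count of two-grade rises at any time in the study, and SAP 2.15 sets the mid-cohort trigger on the primary endpoint, which covers four weeks. The display keeps to Day 1–15, the window of rows 1 and 2. What remains is that Table 2-6 does not name the any-time count among the committee's outputs.
- *The categories depart from Table 3-1 throughout.* The above-normal limb uses 2 × baseline and matches rows 1 and 2.

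The reply does not reach the two core facts. The normal-baseline limb differs from the source it cites, and a planned count has disappeared without a declared change. SAP 2.1 says no separate committee SAP is needed because its methods are those of this SAP, so the wording here carries weight.

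**Conclusion.** The point holds as a defect of specification in one limb of one category, together with one undeclared omission.

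The size of the category mismatch rests on grade limits that the documents do not print. For an assumed grade 1 start of 1.0, 1.25 or 1.5 × ULN, normal-baseline patients peaking between that value and 2 × ULN are in category 1 although Table 3-1 puts them in the Day 15 row. The direction is over-flagging. It would not be a safe assumption if grade 1 started above 2 × ULN, which lies outside the range examined. The omission of the 2 × ULN / 2 × baseline count rests on no assumption.

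Nothing here shows that an escalation decision was wrong.

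**What to change.** 1. In SAP 2.8.2, reconcile the Day 1–15 category 1 with the limits already in Table 3-1: at least 2 × ULN for a normal baseline, and at least 2 × baseline for a baseline above ULN. State that category 1 is assigned only when category 2 is not met. If a grade-based category was intended, the SAP should stop citing Table 3-1 as its basis and explain the difference in section 4.
2. Add the Protocol 9.5.2.2 count (at least 2 × ULN if baseline is normal, 2 × baseline if above ULN) to SAP Table 2-2, or declare and justify its removal in section 4.
3. Name the existing any-time two-grade count in Table 2-6, so that row 3 can be read from the committee's outputs. It should stay a separate output, because categories 0/1/2 are a Day 1–15 variable.

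The cost is a few lines of SAP text and a little programming on data already collected. The latest SAP update is dated after database lock, so the change would be a short addendum. Item 2 bears on the final report even if all escalation decisions are past.

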### 2.8.3 Other safety data

#### 2.8.3.1 ECG and cardiac imaging data

The following quantitative variables will be summarized for averaged triplicate ECG: heart rate, RR interval, PR interval, QRS interval, QT interval and QTcF. Summary statistics for change from baseline will be presented for ECG variables by timepoint and treatment group.

QT intervals will be summarized categorically by computing the number and percentage of patients at each time point and at the maximum post baseline value for the following categories:

- QT, QTcF
  - New  $> 450$  and  $\leq 480$  ms
  - New  $> 480$  and  $\leq 500$  ms
  - New  $> 500$  ms
  - Increase from baseline of  $> 30$  ms to  $\leq 60$ ms
  - Increase from baseline of  $> 60$  ms
- HR
  - Increase from baseline  $>25\%$  and to a value  $> 100$  bpm
  - Decrease from baseline  $>25\%$  and to a value  $< 50$  bpm
- PR
  - Increase from baseline  $>25\%$  and to a value  $> 200$  ms
  - New value of  $> 200$  ms

- QRS
  - Increase from baseline >25% and to a value > 120 ms
  - New > 120 ms

A line plot by patient (Spaghetti plot) will be provided by cohort, visit and treatment group.

In addition, shift tables comparing baseline ECG results (normal, abnormal, not available, total) with the post-baseline results will be provided by visit and at the worst post-baseline result (normal, abnormal, not available, total).

A listing of all newly occurring or worsening abnormalities will be provided, as well as a by-patient listing of all quantitative ECG parameters.

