9.5.2.4 ECGs

[figure not shown]
[figure not shown]
Descriptive summary statistics for the baseline, each study visit, and change from baseline to each study visit will be presented for heart rate, PR interval, QRS interval, RR interval, QT interval and QTcF (QT interval corrected for heart rate according to Fridericia). Number and percentage of patients with abnormal values (such as QTc $>$ 480 ms and $>$ 500 ms or HR $<$ 50 /min) and changes from baseline (such as increases in QTc for ≥ 30 ms and ≥ 60 ms) will be tabulated at each time point and at the maximum value by treatment group in the form of a categorical analysis.

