## 4 Change to protocol specified analyses

NA.

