**Table 5-6 Analysis visit windows based on study day and time**

Analysis Visit	Analysis timepoint	Analysis window for assessment group			
		Temperature/ Parasite count	ECG		PK
			KAE609	Coartem	
Baseline	0 hrs	up to 0 hrs	up to < 0 hrs	up to < 0 hrs	NA
Day 1	1 hrs	NA	NA	NA	>0 to 1.5 hrs
	2 hrs	>0 to 3 hrs	NA	NA	>1.5 to 3 hrs
	4 hrs	>3 to 6 hrs	>0 to 8 hrs	NA	>3 to 5 hrs
	6 hrs	NA	NA	>0 to 37 hrs	>5 to 7 hrs
	8 hrs	>6 to 10 hrs	NA	NA	>7to 10 hrs
	12 hrs	>10 to 18 hrs	>8 to 18 hrs	NA	>10 to 18 hrs
Day 2	24 hrs	>18 to 30 hrs	>18 to 38 hrs	NA	>18 to 38 hrs
	36 hrs	>30 to 42 hrs	NA	NA	NA
Day 3	48 hrs	>42 to 54 hrs	NA	NA	>38 to 49 hrs

	50 hrs	NA	NA	NA	>49 to 51 hrs
	52 hrs	NA	>38 to 56 hrs	NA	>51 to 54 hrs
	56 hrs	NA	NA	NA	>54 to 58 hrs
	60 hrs	>54 to 66 hrs	>56 to 66 hrs	NA	>58 to 64 hrs
	68 hrs	NA	NA	>37 hrs to Day13	>64 to 70 hrs
Day 4	72 hrs	>66 hrs to Day 4	>66 hrs to Day 16	NA	>70 hrs to Day 6
Day 5	NA	Day 5-6	NA	NA	NA
Day 8	NA	Day 7 – 9	NA	NA	Day 7 – 9
Day 11	NA	Day 10 – 13	NA	NA	NA
Day 15	NA	Day 14 – 16	NA	NA	NA
Day 22	NA	Day 17 – 25	NA	NA	NA
Day 29/end of study	NA	Day 26 and above	Day 17 and above	Day 14 and above	NA

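### SAP 2.8.3.1: worst-value ECG percentages rest on up to seven ECG windows for KAE609 but three for Coartem; separately, the SAP's heart-rate and QTc rows depart from the protocol's named cut-offs without saying so

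*SAP*

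**What the plan says.** **Maximum-value categories.** SAP 2.8.3.1 classifies QT, QTcF, heart rate, PR and QRS by the "number and percentage of patients at each time point and at the maximum post baseline value". The rule comes from Protocol 9.5.2.4, where abnormal values and changes "will be tabulated at each time point and at the maximum value by treatment group".

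**ECG windows.** SAP Table 5-6 lists these post-dose windows:
- KAE609: 4, 12, 24, 52, 60 and 72 h and Day 29. The last two are ">66 hrs to Day 16" and "Day 17 and above".
- Coartem: 6 h, 68 h and Day 29. The last two are ">37 hrs to Day13" and "Day 14 and above".

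**Cut-offs.**

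| Item | Protocol 9.5.2.4 (given as examples) | SAP 2.8.3.1 |
|---|---|---|
| Low heart rate | below 50/min | below 50 bpm and a fall of more than 25% |
| QTc increase, lower | at least 30 ms | more than 30, up to 60 ms |
| QTc increase, upper | at least 60 ms | more than 60 ms |
| Absolute QTc | above 480 and above 500 ms | new values only: above 450 to 480, above 480 to 500, above 500 ms |

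Protocol 6.5.5 also uses an increase of at least 60 ms for its site action, and the Amendment 1 log says that limit was corrected to agree with 9.5.2.4. SAP Section 4, "Change to protocol specified analyses", reads NA.

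**The concern.** There are two separate points.

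1. A worst value taken over more readings is more extreme on average, even when nothing differs between the drugs. Protocol 3.2 makes Coartem the reference for judging whether events come from KAE609 or from malaria. QTc prolongation is a listed safety topic in SAP Table 2-1, and SAP 2.8.1.1 selects QTcF and heart rate for the in-text table. A reader who sets the two drugs' percentages at the maximum side by side could take a difference in schedule for a drug effect.

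2. The SAP replaces the only cut-offs that the protocol names and does not record this. Some patients who meet the protocol's low-heart-rate example are not counted in the SAP's row.

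**Working it through.** The documents give no expected rate of ECG abnormality, so there is no figure of the plan's own to reproduce.

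**1. Unequal number of windows**

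Inputs: 7 KAE609 and 3 Coartem windows (SAP Table 5-6). The KAE609 count for single-dose arms (six of the nine regimens) cannot be confirmed. The body of Protocol Table 6-1 was not in the text reviewed, and its footnote 11 exempts one-day regimens from some items. Five windows is therefore run as an illustrative alternative. Assumptions, not from the documents: a chance p of an abnormal value at each window, equal in both groups (no drug effect), and a within-patient correlation r.

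With independent windows, P(worst value abnormal) = 1 − (1 − p)^k:

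- p = 1%: k = 7 gives 6.79%, k = 3 gives 2.97%; ratio 2.29
- p = 2%: k = 7 gives 13.19%, k = 3 gives 5.88%; ratio about 2.25
- p = 5%: k = 7 gives 30.17%, k = 3 gives 14.26%; ratio 2.12

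Readings within a patient are correlated, which shrinks the effect. Simulation with equally correlated normal values, p = 2%:

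| r | 7 windows | 5 windows | 3 windows | ratio 7:3 | ratio 5:3 |
|---|---|---|---|---|---|
| 0 | 13.18% | 9.59% | 5.87% | 2.25 | 1.63 |
| 0.5 | 9.55% | 7.55% | 5.12% | 1.87 | 1.47 |
| 0.9 | 4.65% | 4.14% | 3.39% | 1.37 | 1.22 |

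The smallest ratio run (p = 5%, r = 0.9, five windows) is 9.47/7.96 = 1.19.

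A second simulation worked on the millisecond scale: maximum visit value minus baseline, independent normal noise of equal SD at baseline and each visit, no drug effect. The SDs are assumed. Chance of a maximum increase above 30 ms:

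| SD | 3 ECGs | 5 ECGs | 7 ECGs | ratio 7:3 | ratio 5:3 |
|---|---|---|---|---|---|
| 10 ms | 4.4% | 6.5% | 8.2% | 1.86 | 1.48 |
| 12 ms | 9.3% | 13.3% | 16.4% | 1.76 | 1.43 |
| 15 ms | 17.8% | 24.2% | 29.0% | 1.63 | 1.36 |

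With three windows in each group, both give 5.9% at p = 2% with independence, a ratio of 1.0.

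**2. Low heart rate**

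For baseline b and later value h below 50, the SAP ECG row needs (b − h)/b > 0.25, that is b > h/0.75. The vital-signs rule in SAP Table 2-3 needs pulse at or below 50 with a fall of at least 15, that is b ≥ h + 15.

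| h (bpm) | SAP ECG row counts if b exceeds | Table 2-3 counts if b is at least |
|---|---|---|
| 49 | 65.3 | 64 |
| 48 | 64.0 | 63 |
| 45 | 60.0 | 60 |
| 40 | 53.3 | 55 |

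Example: 60 to 48 bpm is a fall of 12 bpm, and 12/60 = 20%. It meets the protocol's example and neither SAP rule. By contrast, 64 to 49 bpm (15 bpm, 23.4%) misses the ECG row but meets Table 2-3 if the pulse agrees with the ECG rate.

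**3. QTc increase**

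Only values exactly at a limit move: 30 ms drops out and 60 ms falls into the lower band. With illustrative normal changes recorded to 1 ms:

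| Mean, SD | At least 30 ms | More than 30 ms | At least 60 ms | More than 60 ms |
|---|---|---|---|---|
| 5, 12 | 2.059% | 1.679% | 0.000% | 0.000% |
| 10, 15 | 9.680% | 8.586% | 0.048% | 0.038% |
| 15, 15 | 16.686% | 15.072% | 0.151% | 0.121% |

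The loss is 0.4 to 1.6 percentage points at 30 ms and at most 0.03 at 60 ms.

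**The case against.** **On the maximum.** It is specified in the protocol, and results by time point stand beside it. Protocol 9.5 rules out statistical comparison with Coartem for secondary variables, and SAP Table 2-5 marks none for ECG abnormality. The maximum over all KAE609 ECGs errs towards detecting a signal, which is reasonable in a safety study. All of this stands, and it limits the point to how a descriptive table is read. It does not remove it: only Day 29 is a nominal time in both schedules, so the by-time-point tables give little direct comparison, and nothing in the SAP warns about the maximum column.

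**On the cut-offs.** The protocol offers its limits as examples, and settling the final categories is the SAP's job. The SAP also adds a band above 450 to 480 ms. Restricting absolute QTc to new values should remove few patients, because screening excludes QTcF above 450 ms (males) or 460 ms (females). This stands as a reason to call the QTc change slight. The protocol's limits are still the only ones it names, so replacing them merits an entry in Section 4.

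**Stronger readings to avoid.**
- A reader might infer that the changed cut-offs misstate KAE609 against Coartem. They apply equally to every arm and lower counts in all of them.
- A reader might infer that patients with bradycardia vanish from the report. SAP 2.8.3.1 also provides individual line plots, shift tables and a by-patient listing of all quantitative ECG values, and Table 2-3 catches falls of 15 bpm or more to a pulse of 50 or below. What is lost is a count in one summary row.
- A reader might link the row to treatment stopping. Protocol 5.6.2 refers to clinically significant, symptomatic bradycardia in the individual patient, not to this table.

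**Conclusion.** Both points hold as minor, inexpensive corrections.

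1. Percentages at the maximum are not like for like. With no drug effect, KAE609's can be about 1.2 to 2.3 times Coartem's. That range rests on assumed per-window rates of 1% to 5%, correlations of 0 to 0.9, and five or seven KAE609 ECGs. The upper end needs all seven windows and nearly independent readings. The documents give neither the correlation nor the noise, and the single-dose ECG count is unconfirmed.

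2. The SAP departs from the protocol's named heart-rate and QTc limits without declaring it. The heart-rate row is the material part. Falls of less than 15 bpm to a value below 50, from baselines under 64, can escape both summary rules. How many patients that affects cannot be told from the documents. The QTc part is slight.

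The documents do not support a claim that the ECG table as a whole is tilted against KAE609. The first point can raise KAE609's percentages at the maximum, while the second lowers counts in every arm.

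**What to change.** In SAP 2.8.3.1:

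- Keep the maximum-value table over all ECGs. State beneath it the number of scheduled post-dose ECGs per arm, single-dose and three-day arms separately, and caution against direct comparison with Coartem.
- Add a supplementary maximum over equal numbers: one early ECG (KAE609 4 h, Coartem 6 h), one late ECG (KAE609 72 h, Coartem 68 h) and Day 29.
- Say in its footnote that this equalises the count, not the time since dosing. Coartem 68 h is 8 h after its last dose at 60 h (Protocol 5.5.4). KAE609 72 h is about 24 h after a third daily dose, or 72 h after a single dose. The summary also drops KAE609 readings such as 52 h, about 4 h after a third dose, so it could dilute a real effect and must not replace the full table.
- Add rows for heart rate below 50/min as an absolute value and for QTc increases of at least 30 and at least 60 ms. Keep the SAP's combined heart-rate rule as an extra row.
- Replace NA in SAP Section 4 with a short record of the changed categories.

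The cost is SAP wording, a few rows and one small table, with no new ECGs. The SAP history already shows an update after database lock (07-Apr-2020), so additions made after lock should be labelled post hoc.
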